### 3.6.4 Subject Follow-up and Contact

All subjects who are assigned a subject identification number and receive study vaccine will be followed according to the protocol unless consent is withdrawn.

Subjects will be instructed to contact a study team member to report new diagnoses or new or worsening adverse events and to come to the study clinic if medical attention is needed, provided the urgency of the situation permits. For emergencies and other unscheduled visits to a medical facility other than the study clinic, medical records will, to the extent possible, be obtained by the investigator.

Study visits will be scheduled out of school hours (if applicable) whenever possible. During each clinic visit, subjects will be reminded to notify a study team member of the following:

- The occurrence of AEs and SAEs during the respective reporting periods
- Receipt of any concomitant medications during the applicable reporting period
- Plans to move or if contact information changes
- If the subject has decided to withdraw from the study
- Change in general health status
- Any other change in status that may affect the subject’s participation (e.g., plan to participate in another clinical trial)

All deviations from protocol procedures, evaluations, and/or visits will be documented according to the Case Report Form Guidelines provided by Aeras Data Management or their designee. When possible, missed visits and procedures must be rescheduled and performed at the nearest possible time point to the original schedule.

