## 5.5. PER PROTOCOL ANALYSIS SET

The Per Protocol analysis set is defined as all participants in the Modified Intent-to-treat analysis set who received all relevant doses of BCG, H4: IC31 or Placebo and had no major protocol deviations.

A participant will be included in the Per Protocol analysis set if the participant:

- Is included in the Modified Intent-to-treat analysis set.
- Received all relevant doses, based on the date of study vaccination as recorded on Exposure (Day 0) and Exposure (Day 56) eCRFs:
  - o BCG: Day 0.
  - o H4:IC31 or Placebo: Day 0 and Day 56.
- Did not have any major protocol deviations as recorded on the Protocol Deviation eCRF and agreed with Aeras prior to the relevant unblinding activities of the analysis/study.
- Did not have a treatment deviation as identified in collaboration with the clinical trial manager (CTM) in accordance with the Aeras/QuintilesIMS Process Instruction Treatment Deviation Identification and Authorization document.
- Out-of-window QFT-GIT positive results should not be included in the analysis for the PP analysis set.

Refer to the relevant Blind Data Review (BDR) documentation for additional details.

Document: Aeras\_C-040-404\_SAP\_V2\_0

Author: [name]

Version Number:

2.0

Version Date:

29SEP2017

Template No: CS\_TP\_BS016 – Revision 3

Reference: CS\_WI\_BS005

Effective Date: 01May2012

Copyright © 2012 Quintiles Transnational Corp. All rights reserved.

The contents of this document are confidential and proprietary to Quintiles Transnational Corp. Unauthorized use, disclosure or reproduction is strictly prohibited.

The Per Protocol analysis set will be based on the participant level flag assigned in Appendix 1 of the BDR report, as authorized by Aeras prior to DB lock.

Efficacy analyses will also be performed using the Per Protocol analysis set as a sensitivity analysis.

---

Document: Aeras\_C-040-404\_SAP\_V2\_0

Author: [name]

Version Number:

2.0

Version Date:

29SEP2017

Template No: CS\_TP\_BS016 – Revision 3

Reference: CS\_WI\_BS005

Effective Date: 01May2012

Copyright © 2012 Quintiles Transnational Corp. All rights reserved.

The contents of this document are confidential and proprietary to Quintiles Transnational Corp. Unauthorized use, disclosure or reproduction is strictly prohibited.

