### 14.1.3. DERIVATIONS

Based on the aforementioned, the following variables, as presented in the planned TLF shells, will be derived for post-vaccination visits and/or time points:

- QFT-GIT testing compliance derived per visit:
  - o Yes: QFT-GIT assessment date is within the protocol-defined visit window.
  - o No: QFT-GIT assessment date is outside the protocol-defined visit window.
  - o Missing: The participant is expected to have a QFT-GIT assessment available.
  - o Refer to APPENDIX 8: Protocol-defined Visit Windows for the relevant protocol-defined visit windows.
- QFT-GIT result classification at each visit (use the retest result if available). The Investigator's assessment will be used, which is based on the algorithm below.

QFT-GIT Result Classification	QFT Nil	QFT Ag - QFT Nil	QFT Mitogen - QFT Nil
Positive	≤ 8.0	≥ 0.35 (primary analysis threshold) and ≥ 25% of QFT Nil value	Any
Negative		< 0.35 (primary	≥0.5

Document: Aeras\_C-040-404\_SAP\_V2\_0

Author: [name]

Version Number:

2.0

Version Date:

29SEP2017

Template No: CS\_TP\_BS016 – Revision 3

Reference: CS\_WI\_BS005

Effective Date: 01May2012

Copyright © 2012 Quintiles Transnational Corp. All rights reserved.

The contents of this document are confidential and proprietary to Quintiles Transnational Corp. Unauthorized use, disclosure or reproduction is strictly prohibited.

QFT-GIT Result Classification	QFT Nil	QFT Ag - QFT Nil	QFT Mitogen - QFT Nil
Indeterminate		analysis threshold) OR ≥ 0.35 (primary analysis threshold) and < 25% of QFT Nil value	< 0.5
Indeterminate	> 8.0	Any	Any

- If the QFT-GIT result is indeterminate at any of the visits Day 84, M6, M9, M12, M15, M18, M21, M24, M27 or M30, the QFT-GIT test will be repeated (QUANT2 form in the eCRF used to record the result). If the repeat result is negative or indeterminate, the participant will continue with the study visits as if the participant did not convert, and the result for the corresponding visit will be deemed “negative”.
- Any QFT-GIT conversion status:
  - o The QFT-GIT conversion status is assigned hierarchically in the order provided below:
    - Yes: Participant has at least one positive QFT-GIT result classification, regardless of missing or indeterminate results at any other visit and regardless of at which visit the positive QFT-GIT result is recorded.

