      - Post-Day 84 QFT-GIT conversion: First positive QFT-GIT result classification recorded post-Day 84.
      - Early QFT-GIT conversion: First positive QFT-GIT result classification recorded at Day 84.
    - No: Participant has no positive QFT-GIT result classification and the last available QFT-GIT result classification is negative.
    - Missing: Participant has no positive/negative/indeterminate QFT-GIT result classification available.
- Censored:
  - o Participants who do not experience a primary endpoint or early conversion (early conversion is only applicable to the analyses based on the Randomized analysis set), will be censored at the date of their last available, non-positive QFT-GIT result.
  - o The following SAS code will be implemented for all Kaplan-Meier analyses, where:
 

```
PROC LIFETEST DATA = <>;
    TIME Months*Censored(1);
    TEST Treatment_Group;
RUN;
```

    - Censored = 1 represents censored participant.
    - Censored = 0 represents participant who experienced an event.
    - Months represent the available follow-up time (months) per participant since:
      - Day 84 (applicable to analyses based on the mITT and PP analysis set).
      - Randomization (applicable to analyses based on the Randomized analysis set).
- Event:
  - o Participants who experience a primary endpoint or early conversion will be indicated as having an event (depending on the relevant table, early converters will be included/excluded from the participants experiencing an event).

Document: Aeras\_C-040-404\_SAP\_V2\_0

Author: [name]

Version Number:

2.0

Version Date:

29SEP2017

Template No: CS\_TP\_BS016 – Revision 3

Reference: CS\_WI\_BS005

Effective Date: 01May2012

Copyright © 2012 Quintiles Transnational Corp. All rights reserved.

The contents of this document are confidential and proprietary to Quintiles Transnational Corp. Unauthorized use, disclosure or reproduction is strictly prohibited.

- Available follow-up time (months) until first QFT-GIT conversion:
  - o The number of months of follow-up time will be derived for each participant based on the date of randomization/Day 84 (depending on the relevant table) and either the censor or event date.
  - o 1 month = 4 weeks.
  - o For the sensitivity analysis the follow-up time will be rounded to the nearest 6-month interval for any of the following visits:
    - Month 6.
    - Month 12
    - Month 18.
    - Month 24.

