## 14.2. SECONDARY EFFICACY

### 14.2.1. SECONDARY EFFICACY ENDPOINT

The secondary efficacy endpoint is defined as sustained QFT-GIT conversion without reversion:

- Occurrence of a primary endpoint.
- Sustained conversion without a change in QFT-GIT from positive to negative through 6 months after QFT-GIT conversion, also using the threshold of 0.35 IU/mL.
- Sustained conversion without a change in QFT-GIT from positive to negative through 6 months after QFT-GIT conversion, using the alternative threshold of 0.2 at any time point prior to conversion and > 0.70 at initial post-Day 84 QFT-GIT conversion, and maintains QFT-GIT > 0.7 for 6 months after initial conversion.

A participant will be considered as having a secondary endpoint (at the first conversion date), denoted here as '6-month sustained conversion (per protocol)', if that participant had three consecutive positive QFT-GIT results after Day 84.

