### 14.2.3. DERIVATIONS

Based on the aforementioned, the following variables (refer to Section 14.1.2: Analysis of Primary Efficacy Endpoint), as presented in the planned TLF shells, will be derived at 3 and 6 months post first QFT-GIT conversion for participants who have a post-Day 84 QFT-GIT conversion (primary endpoint):

- QFT-GIT result classification (refer to Section 14.1.3: Derivations).
- QFT-GIT 6-month sustained conversion status:
  - o Yes: At both 3 and 6 months following first QFT-GIT conversion, QFT-GIT result classifications are derived as positive.
  - o No: At 3 and/or 6 months following first QFT-GIT conversion, QFT-GIT result classification is derived as negative.
  - o Missing: None of the aforementioned QFT-GIT result classifications (yes, no) has been assigned at 3 or 6 months post-conversion, QFT-GIT result classification is derived as missing.
- Censored:
  - o Participants who do not experience an initial QFT-GIT conversion will be censored at the date of their last available, non-positive QFT result.
  - o Converters who do not have a sustained conversion will be censored at their last available QFT-GIT result.
  - o Converters with only a 3-month post-conversion result and no 6-month post-conversion result will be censored at:
    - The initial conversion visit if the 3-month post-conversion result is positive.

---

Document: Aeras\_C-040-404\_SAP\_V2\_0

Author: [name]

Version Number:

2.0

Version Date:

29SEP2017

Template No: CS\_TP\_BS016 – Revision 3

Reference: CS\_WI\_BS005

Effective Date: 01May2012

Copyright © 2012 Quintiles Transnational Corp. All rights reserved.

The contents of this document are confidential and proprietary to Quintiles Transnational Corp. Unauthorized use, disclosure or reproduction is strictly prohibited.

- The 3-month post-conversion visit if that 3-month post-conversion result is negative.
  - o The following SAS code will be implemented for all Kaplan-Meier analyses, where:

```
PROC LIFETEST DATA = <>;
    TIME Months*Censored(1);
    TEST Treatment_Group;
RUN;
```

- Censored = 1 represents censored participants.
      - Censored = 0 represented participants who experienced an event (sustained QFT-GIT conversion).
      - Months represent the available follow-up time (months) per participant since Day 84.
  - Event:
    - o Participants, who experience a sustained QFT-GIT conversion for three consecutive visits will be indicated as having an event.

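### The Per Protocol analysis drops out-of-window QFT-GIT results only when they are positive, so the exclusion depends on the outcome

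*SAP*

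**What the plan says.** SAP 5.5 lists the conditions for the PP set and ends the list with a rule about results rather than participants: "Out-of-window QFT-GIT positive results should not be included in the analysis for the PP analysis set". It then refers to the Blind Data Review documentation for detail and bases the set on a participant-level flag from that review.

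SAP 14.1.3 defines testing compliance by date, whatever the result: "No: QFT-GIT assessment date is outside the protocol-defined visit window". The windows are in Appendix 8.

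Negative results carry no window condition in the derivations. Participants without a primary event "will be censored at the date of their last available, non-positive QFT-GIT result" (SAP 14.1.3). Sustained status in SAP 14.2.3 is "Yes: At both 3 and 6 months following first QFT-GIT conversion, QFT-GIT result classifications are derived as positive" and "No: At 3 and/or 6 months following first QFT-GIT conversion, QFT-GIT result classification is derived as negative". SAP 14.2.1 words the same endpoint differently: it is met "if that participant had three consecutive positive QFT-GIT results after Day 84".

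The protocol's own PP definition (7.1) asks for all doses and no major deviations, and has no result-level rule. PP is a sensitivity analysis. The primary table (SAP 14.1.2), the sustained-conversion tables at both thresholds (14.2.2) and the reversion table (14.3.2) are repeated for it.

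**The concern.** Two tests taken equally late are treated differently only because one is positive and the other negative. A window rule is meant to standardise timing; this one also filters on the endpoint. It lowers PP event counts, and a reader comparing PP with mITT could not tell whether a difference came from protocol adherence or from the deletion of observed events.

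Late tests are foreseeable. Protocol 3.6.4 says "When possible, missed visits and procedures must be rescheduled and performed at the nearest possible time point to the original schedule", and the SAP plans a table that counts out-of-window tests. The rule weighs most on sustained conversion, because status Yes needs three positives in a row of visits and losing any one of them is enough to lose the event. The SAP also does not say whether a dropped first positive deletes the primary event or moves it to a later in-window positive, so two programmers could report different PP counts.

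**Working it through.** The documents give no out-of-window rate and no PP figure to reproduce. The inputs are the rule in SAP 5.5, the derivations in SAP 14.1.3 and 14.2.3, and, from Protocol 7.6, 10% conversion per year, 7% loss per year and 20% reversion over one year (used here as the assumed share of converters who revert). The assumption is that a share w of tests is late, w = 0.05 or 0.10, equal in all arms.

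**1. How each late test is treated in PP**

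| Late test | If positive | If negative |
|---|---|---|
| First conversion visit | Removed; event deleted or delayed, not stated | Kept; can set the censoring date |
| 3 months after conversion | Removed; with a positive 6-month test the status is neither Yes nor No, so Missing | Kept; status No |
| 6 months after conversion | Removed; with a positive 3-month test, censored at: "The initial conversion visit if the 3-month post-conversion result is positive" | Kept; status No |

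**2. Direction at 0.35 IU/mL.** All sequences of positive, negative and missing results after a first conversion at Months 6, 12, 18 or 24 were enumerated, with the call-back test for Month 6 and 12 converters and every set of late visits: 936 combinations. Removing late positives raised conversions in 0 and lowered them in 300. It raised sustained conversions in 0 and lowered them in 96 to 148, depending on how consecutive is read. PP membership requires a Day 84 negative, so dropping a Day 84 positive adds nobody.

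**3. Alternative-threshold sustained endpoint.** SAP 14.2.1 asks for a value above 0.70 at the initial conversion. Take a Month 6 converter at 0.50, late, then above 0.70 at Months 9, 12 and call-back, with the low earlier value also required. Read literally this is not an event in mITT. If PP drops the 0.50 and lets Month 9 become the initial conversion, it is an event.

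**4. Sustained conversions kept (SAP 14.2.3)**
- Independent lateness: (1 − w)³ = 0.95³ = 0.857 and 0.90³ = 0.729, so losses of 14% and 27%.
- Same participants always late: 1 − w = 0.95 and 0.90, so losses of 5% and 10%.
- Interval width for the log hazard ratio scales as 1/√(share kept): 1.080 and 1.171 (independent), 1.026 and 1.054 (always late).
- On the wording of 14.2.1, an early converter with a positive call-back test, for which Appendix 8 lists no window, can lose one positive and still qualify. The share kept is (1 − w)³ + 3w(1 − w)² = 0.993 and 0.972.

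**5. Primary conversions kept**
- Event deleted: 0.95 and 0.90.
- Later in-window positive counts, 80% of converters positive at all three tests and 20% negative at both repeats: 0.8(1 − w³) + 0.2(1 − w) = 0.990 and 0.979. Other reversion patterns lose less.

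**6. Vaccine efficacy (VE).** If fractions f_v and f_p of events are lost in the vaccine and placebo arms, apparent VE ≈ 1 − (1 − VE)(1 − f_v)/(1 − f_p). Equal fractions cancel. A simulation of 1,000,000 per arm (true hazard ratio 0.5, independent w = 0.10 in every arm) gave these hazard ratios:
- Primary: 0.503 in mITT; in PP, 0.502 if the event is deleted and 0.511 if a later positive counts.
- Sustained: 0.505 in both.

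Unequal assumed losses move VE either way. With true VE 0, 15% vaccine and 5% placebo give 1 − 0.85/0.95 = +0.105; the reverse gives 1 − 0.95/0.85 = −0.118.

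**7. Cost of a symmetric censoring rule.** Suppose PP censors at the first late test whatever its result. An event at the k-th visit then survives with probability (1 − w)^k. With 10% conversion and 7% loss per year from Day 84, events split about 0.161, 0.302, 0.279 and 0.258 over Months 6, 12, 18 and 24.
- w = 0.05: 0.161×0.95 + 0.302×0.9025 + 0.279×0.8574 + 0.258×0.8145 = 0.875, a loss of about 12.5%.
- w = 0.10: 0.161×0.90 + 0.302×0.81 + 0.279×0.729 + 0.258×0.6561 = 0.762, a loss of about 24%.

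**The case against.** The strongest reply is that little is at stake. PP is only a sensitivity analysis, mITT carries the efficacy analysis, and with equal lateness the hazard ratios hardly move. That stands, and it limits the point to PP counts, rates and precision.

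The operating detail may sit in the Blind Data Review documentation, and procedures done out of window are a deviation category in SAP section 9 without regard to the result, so late negatives might be removed there. This is possible, but nothing shown says so. The review assigns a participant-level flag, which does not remove single results. If the bullet itself is read at participant level, someone is excluded for a late positive and kept for an equally late negative, which still selects on outcome.

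The lateness rates are assumed, and the nearest possible date for a missed test may still fall inside a 28-day window. That stands too: the percentages are illustrations.

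A reader might infer that the rule favours the vaccines. The documents do not support that. BCG allocation is known to participants and clinic staff, so unequal attendance is conceivable, but no data show it and the bias has no fixed sign. A reader might also infer that the rule can never add an event. That holds at 0.35 IU/mL but not with certainty for the alternative-threshold endpoint. SAP 14.3.3 substitutes the threshold in the result classification, which would remove the exception, but that is the exploratory section and 14.2.1 does not refer to it.

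**Conclusion.** The PP rule in SAP 5.5 is outcome-dependent as written. At the 0.35 IU/mL threshold it can only lower or keep conversions and 6-month sustained conversions; at the alternative threshold a literal reading leaves one route by which an event could be gained.

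The cost is lower PP rates and wider PP intervals. It is largest for sustained conversion as derived in SAP 14.2.3: 14% or 27% fewer events at an assumed, independent 5% or 10% lateness per test, and 5% or 10% if the same participants are always late. VE is essentially unbiased when lateness is equal across arms. The mITT analyses have no such rule and are unaffected. The finding rests on the SAP text; the Blind Data Review documentation could add to it.

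**What to change.** Delete the bullet in SAP 5.5 and analyse all QFT-GIT results in PP at their actual dates, as in mITT. This changes one line, loses no data and leaves mITT as it is.

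If a window restriction is wanted in PP, apply it whatever the result, and state how a removed result affects the conversion date, the censoring date and sustained status. Censoring at the first out-of-window test would be symmetric, but at 5% or 10% lateness it would lose about 12.5% or 24% of primary events, against 5% or 10% under the present rule if a dropped first positive deletes the event. Deletion of the bullet is therefore preferred.

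Separately, correct Appendix 8. Its Month 27/30 row counts from an initial conversion at Month 30, whereas the schedule footnotes provide post-conversion visits for conversions at Months 6 to 24. Read literally, the repeat tests of Month 24 converters have no listed window. This is one table row.

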## 6. GENERAL CONSIDERATIONS

### 6.1. REFERENCE START DATE AND STUDY DAY

Reference start date is defined as the date of first study vaccination and equals Day 0. Study day will be calculated relative to the reference start date and will be used to show start or stop day of an assessment or event. Study day will be calculated as follows:

- If the date of the assessment/event is prior to, on or after the reference start date:
  - o Study day = (date of assessment/event – reference start date).

Unless otherwise specified, if the date of the assessment/event is partial or missing, study day and any corresponding durations will not be calculated and will be presented as missing in the listings.

Some presentations include the study day relative to the most recent vaccination (presented as relative day) and will be calculated as follows:

- If the date of the assessment/event is on or after the most recent vaccination:
  - o Relative day = (date of assessment/event – date of most recent vaccination).

### 6.2. BASELINE

Unless otherwise specified, Baseline is defined as the last non-missing assessment (scheduled or unscheduled) prior to the first study vaccination. In the case where the last non-missing assessment and the reference start date coincide, that assessment will be considered pre-vaccination (Baseline). For example, if vital signs, laboratory or electrocardiogram assessments fall on the date of first study vaccination and the time of the assessment is missing, the applicable assessment will be considered as Baseline. However, adverse events (AEs) starting on the reference start date (date of first study vaccination) will be considered as treatment-emergent, therefore post-baseline.

### 6.3. RETESTS, UNSCHEDULED VISITS AND PREMATURE DISCONTINUATION DATA

In general, for by-visit summaries, data recorded at the scheduled visit will be presented. Unscheduled assessments will not be included in by-visit summaries, but may contribute to the Baseline value.

In the case of a retest (same visit number assigned), the latest available test result as provided in the data transfer for that visit/time point will be used for by-visit summaries.

Listings will include scheduled, unscheduled and premature discontinuation data. No mapping of premature discontinuation data will be performed.

---

Document: Aeras\_C-040-404\_SAP\_V2\_0  
Author: [name]

Version Number: 2.0  
Version Date: 29SEP2017

Template No: CS\_TP\_BS016 – Revision 3  
Effective Date: 01May2012

Reference: CS\_WI\_BS005

